7. SAFETY ANALYSES

The following variables are safety endpoints.

- AEs

- Injection site reactions/local tolerability in selected quadrant (through subject and Investigator reporting)
- Study drug exposure and compliance
- Prior and concomitant medications
- Vital signs
- Laboratory testing
- Immunogenicity data

7.1. Prior, Concomitant, and Follow-up Medications

The World Health Organization (WHO) Drug Dictionary (Version 10MAR2016) will be used to classify prior and concomitant medications by therapeutic class. Prior medication will be defined as any medication with a start date prior to the first treatment start date in study EN3835-202. Concomitant medication is defined as any medication with a start date on or after the first treatment start date in study EN3835-202 and on or before the last dose date. If the medication starts before the first treatment start date in study EN3835-202 and stops on or after the first treatment start date in study EN3835-202, it will be considered as both prior and concomitant medication. If a medication has partial or missing start date and cannot be determined if it is a prior medication based on the start date, it will be considered as a prior medication. If a medication has partial or missing end date and cannot be determined if it is a concomitant medication based on start and end date, it will be considered as a concomitant medication. Any medications started after the last dose date of study drug will be considered as follow-up medications.

Prior, concomitant, and follow-up medication use will be summarized descriptively by the number and percentage of subjects receiving each medication within each therapeutic class. Multiple use of the same medication by a subject will be counted only once. Tables will be sorted by class and preferred term in decreasing frequency of the number of subjects.

7.2. Study Drug Exposure

For those subjects that elect, are eligible, and do receive treatment in study EN3835-202, the number of injections in each treatment session and the reason for the treatment session not done will be summarized by treatment region and overall using appropriate descriptive statistics. If a subject receives more than 1 treatment course in study EN3835-202, each treatment course will be summarized independently.

7.3. Treatment Administration and Compliance

All doses are administered while the subjects are at the investigational site. Any dose that was not administered per protocol will be recorded as a protocol deviation by the Investigator. The number and percentage of subjects treated in each quadrant will be presented in the summary table. The number of injections, number of dimples treated as well as average number of injections per dimple will be tabulated for each treatment session by treatment course and by treatment region. The number of subjects that received 12 injections for all treatment sessions as

well as the number of subjects that didn't receive 12 injections for all treatment sessions will be tabulated by treatment region. Subjects with protocol deviation will be listed. In addition, subjects who did not receive 3 treatment sessions and subjects who didn't receive 12 injections at a treatment session will also be listed separately.

7.4. Adverse Events

Treatment-emergent adverse events (TEAEs) is defined as any AE with onset date on or after the treatment start date in each treatment course in study EN3835-202. TEAEs are defined within each treatment course in study EN3835-202. AEs with missing or partial onset date and cannot be determined in which treatment course it occurred with its onset and end dates will be considered as TEAEs in treatment course 1. AEs with missing or partial onset date and cannot be determined in which treatment session it occurred with its onset and end dates will be considered as earliest treatment course and earliest treatment session possible.

Treatment-related adverse events are TEAEs with a relationship to study medication of possible, probable, or missing.

AEs will be coded using the Medical Dictionary for Regulatory Activities (MedDRA), Version 19.0.

Overall AE summaries for observation phase as well as overall TEAE summaries for treatment phase will be tabulated. Descriptive statistics (the number and percentage) for subjects reporting AEs, TEAEs, and Adverse Events of Special Interest (AESI) will be tabulated by system organ class (SOC) and preferred term (PT); by SOC, PT, and severity; and by SOC, PT, severity and relationship to study drug. TEAE will also be summarized by SOC, PT, and treatment course. The duration of treatment related AE descriptive statistics will be summarized within each PT under each SOC. The TEAE tables will be sorted by SOC and PT in decreasing frequency of the number of subjects in the overall column.

If there are more than 1 AE coded to the same SOC or PT for the same subject under a certain column in the summary table, the subject will be counted only once for that SOC or PT under that column. If there are more than 1 AE coded to the same PT for the same subject, the subject will be counted only once for that PT using the most severe and most related occurrence for the summarization by severity and by relationship to the study drug. If there are more than 1 AE coded to the same PT, the longest AE will be used for that PT for the duration descriptive statistics.

Serious adverse events (SAEs) and AEs leading to premature discontinuation of study drug will be summarized. Listings will be presented for subjects with AEs, SAEs, AESI, AEs leading to discontinuation, and subjects who die (if any).

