14. ASSESSMENT OF SAFETY

14.1. Definitions

14.1.1. Adverse Event

An adverse event (AE) is any unfavorable or unintended change in body structure (signs), body function (symptoms), laboratory result (eg, chemistry, ECG, X-ray, etc), or worsening of a pre-existing condition associated temporally with the use of the study medication whether or not considered related to the study medication. AEs will be captured once a subject has signed the informed consent. AEs include:

- Changes in the general condition of the subject
- Subjective symptoms offered by or elicited from the subject
- Objective signs observed by the Investigator or other study personnel
- All concurrent diseases that occur after the start of the study, including any change in severity or frequency of pre-existing disease
- All clinically relevant laboratory abnormalities or physical findings that occur during the study

A treatment-emergent adverse event (TEAE) is any condition that was not present prior to treatment with study medication but appeared following treatment, was present at treatment initiation but worsened during treatment, or was present at treatment initiation but resolved and then reappeared while the individual was on treatment (regardless of the intensity of the AE when the treatment was initiated).

All AEs, including both observed or volunteered problems, complaints, signs or symptoms must be recorded on the AE page of the eCRF, regardless of whether associated with the use of study medication. This would include AEs resulting from concurrent illness, reactions to concurrent medication use, or progression of disease states (excluding the disease under study). A condition present at baseline that worsens after initiation of study treatment will be captured as an AE; the onset date will be the date the event worsened. The AE should be recorded in standard medical terminology when possible.

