14.4. Intensity Assessment

The intensity (or severity) of AEs is characterized as mild, moderate, or severe:

- **Mild** AEs are usually transient, requiring no special treatment, and do not interfere with the subject's daily activities.
- **Moderate** AEs introduce a low level of inconvenience or concern to the subject and may interfere with daily activities, but are usually ameliorated by simple therapeutic measures.
- **Severe** AEs interrupt a subject's usual daily activity and typically require systemic drug therapy or other treatment.

When the intensity category of an AE changes, the greatest intensity during that continuous episode should be recorded.

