17.6.4. Adverse Events

The MedDRA will be used to code AEs. The version used in this study will be stated in the Data Management Plan.

An AE (classified by preferred term) that started during the treatment period will be considered a TEAE if it was not present prior to the first dose of study drug, or was present prior to the first dose of study drug but increased in intensity during the treatment period. If more than 1 AE is reported prior to the first dose of study drug and coded to the same preferred term, then the AE with the greatest intensity will be used as the benchmark for comparison to the AEs occurring during the treatment period which were also coded to that preferred term. Any AE present prior to the first dose of study drug that increases in intensity during the treatment period will be re-entered with a new start date of the date of increased intensity.

Descriptive statistics (the number and percentage) for subjects reporting TEAEs in each treatment group will be tabulated by system organ class and preferred term; by system organ class, preferred term, and severity; and by system organ class, preferred term, and relationship to study drug. If more than 1 AE is coded to the same preferred term for the same subject, the subject will be counted only once for that preferred term using the most severe and most related occurrence for the summarization by severity and by relationship to the study drug.

SAEs and AEs leading to premature discontinuation of study drug will be summarized by preferred term and dose received. Listings will be presented for subjects with SAEs, subjects with AEs leading to discontinuation, and subjects who die (if any).

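### SAP 7.4 assigns TEAEs to each 202 course by onset date alone, so an AE carried into a repeat EN3835 course that then worsens can be missed in that course

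*Combined protocol and SAP*

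**What the plan says.** The protocol text used here is Amendment 2.

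- **SAP 7.4** counts as treatment-emergent "any AE with onset date on or after the treatment start date in each treatment course in study EN3835-202", and adds that "TEAEs are defined within each treatment course in study EN3835-202". Worsening is not mentioned. Treatment-related AEs are a subset of TEAEs, and one table breaks TEAEs down by SOC, PT and treatment course.
- **Protocol 14.1.1** also counts a condition that "was present at treatment initiation but worsened during treatment". For a condition present at baseline that gets worse, "the onset date will be the date the event worsened".
- **Protocol 17.6.4** also counts an AE that "was present prior to the first dose of study drug but increased in intensity during the treatment period", and gives a data-entry rule: "Any AE present prior to the first dose of study drug that increases in intensity during the treatment period will be re-entered", dated at the increase.
- **Protocol 14.4** says that when intensity changes, "the greatest intensity during that continuous episode should be recorded".
- **SAP section 9** declares two changes from the protocol: cohorts are replaced by phases and populations, and the observation population is redefined. The TEAE definition is not among them.

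**The concern.** One of the SAP's secondary objectives (1.3.2) is the safety of giving EN3835 again, in the same or another quadrant, to a woman already exposed. Worsening of a lingering reaction after re-injection is a signal that objective should pick up. Protocol 14.3 takes the same view: for an AE that carries over into an active treatment phase, causality is judged for that phase only if the AE got worse.

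An onset-only rule picks up worsening only if the AE record is given a new start date when it worsens. The protocol ties that re-dating to baseline or to the first dose of study drug, whereas the SAP counts TEAEs course by course. Where the two anchors differ, a worsened AE can keep an onset that precedes the repeat course. The SAP also drops the re-treatment and re-dosing cohorts, so the by-course table carries the comparison for second 202 courses.

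**Working it through.** The point concerns a definition, and the plan gives no figure to reproduce. The check traces the SAP rule through each situation in which an AE is ongoing when EN3835 is injected and then worsens.

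**Inputs.** A woman may have at most 2 EN3835 courses across 201 and 202 (protocol 12.1.4), so only women who had placebo in 201 can have two courses in 202. At subject level, the SAP's observation phase ends at the first 202 treatment, and its treatment phase runs from there to study end (SAP section 2). SAP 3.2 sets safety baselines for measures such as vital signs and laboratory values at the last value before the first 202 treatment.

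| Case | Re-dating under protocol 14.1.1 or 17.6.4? | Result under SAP 7.4 |
|---|---|---|
| (a) Placebo in 201; AE ongoing before 202 course 1, worsens after injection | Yes. It was present before the first EN3835 dose, so the AE "will be re-entered with a new start date of the date of increased intensity" | Counted in course 1 at the worsened severity |
| (b) EN3835 in 201; AE began after that dose, ongoing at 202 Day 1, worsens after re-injection | Depends on whether the first dose is the 201 or the 202 dose | 202 dose: counted. 201 dose: not a 202 TEAE; peak intensity sits on a record dated before the treatment phase |
| (c) Placebo in 201; AE began in 202 course 1, ongoing at course 2, worsens after course 2 starts | No. It was not present at baseline or before the first dose under either anchor | Not a course 2 TEAE; counted under course 1, in the same treatment phase |
| (d) AE began after session 1, worsens after session 2 or 3 of the same course | Not needed | Already a TEAE of that course |

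Where re-dating does not apply, 14.4 leads to a single record with the old onset date and the greatest intensity. That produces the loss in case (c), and in case (b) if the 201 dose is meant.

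**Effect on the tables.** In case (c) the AE is absent from the course 2 column of the by-course table. It remains in the overall treatment-phase TEAE tables at its greatest severity. In case (b), if the 201 dose is meant, it drops out of the TEAE tables and therefore out of the treatment-related and duration summaries.

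**Is carry-over possible?** Session 3 is on Day 43 and a second course may begin on Day 71 (protocol 10.1): 71 − 43 = 28 days. SAP Table 3, footnote m, also provides for Day 1 of a second course on Day 71 of the one before. Earlier studies report local effects resolving within a mean of 18 days (protocol 8.3.1.1), within 3 weeks (8.3.1.2), and in the majority of cases before the next session (8.3.1.3). A mean and a majority leave room for longer events, but these reports point to few.

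**The case against.** A reader might infer that every AE ongoing at a course start that then worsens is lost. The documents do not support that. The re-dating rules in protocol 14.1.1 and 17.6.4 give a worsened AE a new onset date, and an onset-only definition then counts it at its worsened severity. Case (a) is safe if sites follow those rules ahead of the general instruction in 14.4. The baseline sentence in 14.1.1 does not mention a first dose, and if baseline is taken as in SAP 3.2, just before the first 202 treatment, case (b) is safe too. That stands as a possible reading, but the protocol does not say which dose is meant, so sites could record the same event differently. No such reading rescues case (c), because a course 1 AE arose after both anchors.

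A reader might also infer that peak severity always moves to an earlier phase. In case (c) it moves to an earlier course within the same phase. The text specifies the by-course table by SOC and PT only, so it describes no output showing a severe event under course 1 and none under course 2.

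The objection that case (c) is rare is fair. It needs a woman with two 202 courses. For injection-site events it mainly concerns the same quadrant treated twice, since a reaction in a different quadrant would ordinarily be a new event.

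Two further points stand. The protocol's own abbreviation list defines a TEAE by timing only, so the protocol is not consistent with itself. And the SAP's visits from Day 450 to Day 720 do not appear in Amendment 2, so the SAP may follow a later amendment, not among the pages reviewed, whose TEAE text could differ.

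**Conclusion.** The point holds in a limited form. SAP 7.4 omits a worsening clause that the protocol states twice, and section 9 does not declare the omission. The protocol's re-dating rule makes up for this at the first 202 course of a woman who had placebo. It does not do so for an AE from 202 course 1 that worsens after course 2 starts. For an AE that began after a 201 EN3835 dose, the answer depends on an undefined term.

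The size cannot be computed. It would need the share of women with an AE ongoing at a repeat course start and the share of those AEs that worsen, and the documents give neither. The earlier studies and the gap of at least 28 days suggest the number is small. A reader might go on to infer that re-exposure will look materially safer than it is. Each affected event does lower the repeat-course TEAE count, but nothing in the documents shows that the total would be material.

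This rests on Amendment 2 being the governing protocol text for AEs and on sites keeping one record per continuous episode under 14.4 wherever re-dating is not required. It should be corrected, because it bears on a stated objective and the correction is cheap.

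**What to change.** 1. In SAP 7.4, define a TEAE of a course as an AE whose onset is on or after that course's first injection and before the next course's first injection, or an AE ongoing at that first injection whose intensity increases afterwards. The upper limit also ties each new AE to one course.
2. Require re-entry of a worsened AE, dated at the worsening, at every course start and not only at the first dose. State that the re-entered date is the onset used in analysis.
3. Reconcile this with protocol 14.4, so that the greatest-intensity rule applies within a course and does not merge records across a course start.
4. If onset alone is intended, list that departure in SAP section 9.

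The cost is a change of wording in SAP 7.4 and an eCRF completion note, with possible re-entry of a few events. It should be done before database lock: if only the greatest intensity is stored, the date of worsening may not be recoverable afterwards.

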0. REVISION HISTORY

1. STUDY DESIGN

1.1. Description of Study Design

This clinical study is a multicenter, open-label extension study. Subjects who completed the entire double-blind, placebo-controlled, parent trial (EN3835-201) and sign an informed consent form will be eligible to participate in this study.

After the Sponsor has broken the EN3835-201 study drug blind, subjects enrolled in the open-label study will have the following options:

- To have no EN3835 treatments in study EN3835-202
- If received EN3835 in study EN3835-201, may elect to have a qualifying quadrant other than the one treated with EN3835 in study EN3835-201 (termed *re-dosing*)
- If received EN3835 in study EN3835-201 and the cellulite severity scores of the treated quadrant have returned to or are higher than EN3835-201 baseline scores, may elect to have the previously treated quadrant retreated with EN3835 (termed *re-treatment*)
- If received placebo in study EN3835-201, may elect to have a qualifying quadrant treated with EN3835; also may elect to have a second qualifying quadrant treated with EN3835 after completing the treatment course

Following completion of safety and cellulite assessments at Day 71 of the double-blind study (EN3835-201), subjects will be asked if they wish to continue in the open-label extension to the double-blind study (Screening A). Subjects enrolled in study EN3835-202 who elect to receive EN3835 treatment (either re-treatment, re-dosing, or a first treatment) must meet specific inclusion and exclusion criteria for eligibility during re-screening (Screening B) prior to EN3835 dosing.

Previously placebo-treated subjects will have the option to receive a second course of EN3835 in the same or different qualifying quadrant after at least 28 days following the end of the first treatment course (eg, the Screening B visit of second quadrant could be performed on Day 71 after treating the first quadrant). The selected quadrant can be re-treatment or re-dosing.

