- Observation phase: Observation phase is defined as the time period from Screening A to the first treatment date of the same quadrant in study EN3835-202 or the end of study EN3835-202 if there is no treatment received for the same quadrant in study EN3835-202. Observation phase is defined within each treated quadrant, unless the summary is for subject level only and cannot be differentiated by the treated quadrant, ie, disposition, adverse event (AE). For subject level summaries, observation phase is defined as the time period from Screening A to the first treatment date in study EN3835-202 or the end of study EN3835-202 if there is no treatment received in study EN3835-202.
- Treatment phase: Treatment phase is defined as the time period from the first treatment date of certain quadrant in study EN3835-202 to the end of study EN3835-202. Treatment phase is defined within each treated quadrant, unless the summary is for subject level only and cannot be differentiated by the treated quadrant, ie, disposition, AE. For subject level summaries, treatment phase is defined as the time period from the first treatment date to the end of study EN3835-202.

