3. STATISTICAL METHODS AND CONSIDERATIONS

3.1. Descriptive Statistics

All analysis results will be presented in summary table using appropriate descriptive statistics, unless otherwise stated. The statistics include the number (count) and percentage for all categorical variables. The denominator will be based on the number of subjects in each column group in the summary table, unless otherwise stated. All continuous variables will be summarized with observed count, mean, standard deviation, median, minimum, and maximum value.

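### SAP 7.4 gives each course's TEAE window a start but no end, so the by-course adverse-event percentages rest on follow-up of unequal and undefined length

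*Combined protocol and SAP*

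**What the plan says.** SAP 7.4 takes a TEAE to be "any AE with onset date on or after the treatment start date in each treatment course in study EN3835-202", and adds that "TEAEs are defined within each treatment course in study EN3835-202". It gives no closing date for a course and no rule for passing from course 1 to course 2. SAP 2 does not fill the gap. With AEs as one of its examples, it states: "For subject level summaries, treatment phase is defined as the time period from the first treatment date to the end of study EN3835-202".

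The table is planned in SAP 7.4: "TEAE will also be summarized by SOC, PT, and treatment course". Under SAP 3.1 this means counts and percentages: "The denominator will be based on the number of subjects in each column group in the summary table". Person-time is not mentioned.

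An AE with a missing or partial onset date that its onset and end dates cannot place in a course "will be considered as TEAEs in treatment course 1". One that cannot be placed in a session "will be considered as earliest treatment course and earliest treatment session possible".

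Only former placebo women can have two courses in EN3835-202. SAP 1.1 gives them the "option to receive a second course of EN3835 in the same or different qualifying quadrant after at least 28 days" from the end of the first. Protocol 12.1.4 (Amendment 2) allows former active women one further course.

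On follow-up, SAP 1.1 allows up to one year for each treated quadrant, and protocol 12.5 follows women under treatment at study termination only through Day 71. On collection, protocol 14.5.1 stops recording AEs 30 days after the last dose, whereas SAP Tables 2 to 4 show AEs monitored for the whole study.

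**The concern.** Safety of re-treating or re-dosing is a secondary objective (SAP 1.3.2), and protocol 12.1.4.2 notes that the product is a foreign protein. SAP 9 drops the protocol's analysis by four cohorts. The by-course table is therefore the only AE tabulation in SAP 7.4 that separates a second EN3835-202 course, and readers will compare its columns.

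That comparison makes sense only if each event belongs to one course and each course is watched for the same time. The SAP secures neither. Two programmers could build different tables from the same text, with errors in opposite directions.

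**Working it through.** **Inputs.** Sessions on Days 1, 22 and 43, and a gap of at least 28 days (SAP 1.1). Screening B falls 14 to 1 days before the first injection (SAP Table 3). Follow-up of up to one year is taken as 360 days, the last observation visit. The Day 71 cut-off is in protocol 12.5 and the 30-day limit in protocol 14.5.1. The documents give no AE rates, so every rate below is an assumption.

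**1. Earliest start of course 2.** 43 + 28 = Day 71, which reproduces the Day 71 in protocol 10.1. SAP 1.1 instead puts the Screening B visit on Day 71, so the first injection could come as late as 71 + 14 = Day 85. If course 1 closes the day before, it lasts 70 to 84 days.

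**2. Windows for a two-course woman who starts course 2 on Day 71.**

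| Rule | Course 1 (days) | Course 2 (days) | Ratio 1:2 |
|---|---|---|---|
| Course 1 closes at course 2, full follow-up | 70 | 360 | 0.19 |
| Same, course 2 cut at its Day 71 | 70 | 71 | 0.99 |
| Same, 30-day limit (43 + 30 = Day 73) | 70 | 73 | 0.96 |
| Literal, full follow-up | 70 + 360 = 430 | 360 | 1.19 |
| Literal, course 2 cut at its Day 71 | 70 + 71 = 141 | 71 | 1.99 |

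A single-course woman contributes 73 days to course 1 under the 30-day limit, and up to 360 without it.

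**3. Extreme case, no true difference.** Risk of at least one event = 1 − exp(−rate × days / 365.25).

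| Assumed rate per person-year | 70 days | 360 days |
|---|---|---|
| 0.25 | 4.7% | 21.8% |
| 0.5 | 9.1% | 38.9% |
| 1.0 | 17.4% | 62.7% |

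**4. Dilution in the course 1 column.** If a share q of that column has two courses and the rest are followed for 360 days, then at 0.5 per person-year the column shows q × 9.1 + (1 − q) × 38.9. For q = 0.25, 0.50 and 0.75 this gives 31.5%, 24.0% and 16.6%, against 38.9% in course 2.

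**5. When the direction turns.** If course 2 is cut at Day 71, its risk is 1 − exp(−0.5 × 71 / 365.25) = 9.3%. With q = 0.50 the columns would read 24.0% against 9.3%, so course 1 would look worse.

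**6. Literal reading.** Course-2 events then fall in both columns. With assumed independent per-course risks of 10% and 20%, two-course women show 1 − 0.90 × 0.80 = 28% against 20%. With an assumed 10% risk per 73 days, a true doubling of the rate in course 2 and windows of 141 and 71 days, the columns show 26.4% against 18.5%.

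**7. Undated events.** Take an assumed 20 and 30 events per 100 women, a ratio of 1.50. Moving 2%, 5%, 10% or 20% of course-2 events to course 1 gives ratios of 29.4/20.6 = 1.43, 28.5/21.5 = 1.33, 27/23 = 1.17 and 24/26 = 0.92. The true share is not known.

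**8. Who is in course 1.** Former active women are already re-exposed in their course 1. With assumed risks of 20% on first exposure and 30% on re-exposure, and equal windows, the ratio of course 2 to course 1 falls from 1.50 to 0.30/0.225 = 1.33 if a quarter of course 1 is re-exposed, and to 0.30/0.25 = 1.20 if half is.

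**The case against.** The strongest reply is that SAP 7.4 intends one course per event. It says TEAEs are defined within each course, and its placement rules for undated events would have little purpose if an event could count in two courses. This stands. The literal reading is the less likely one, and the reversal in step 6 depends on it.

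Second, 70 against 360 days pairs the earliest restart with the longest follow-up, and it describes two-course women, not the whole course 1 column. Study termination or the 30-day limit would bring the windows of two-course women close together. This also stands as a limit on size. It does not settle the matter: SAP 7.4 does not apply the 30-day limit, and the SAP schedules contradict it. The SAP also describes visits on Days 450 to 720 that are absent from the Amendment 2 text, so a later protocol version may have changed the limit.

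Third, protocol 8.3.1.2 and 8.3.1.3 describe mainly injection-site events that resolved within three weeks or before the next session. Such events fall inside a 70-day window, so on the better reading they are little affected.

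Fourth, the undated rule is narrow, the table is descriptive with no stated contrast between courses, and AE, SAE and AESI listings are also planned. All true, but listings give no rates, and adjacent columns invite comparison.

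**Conclusion.** The gap is real: no closing date, crude percentages, and no common window or person-time. On the better reading it makes late and background events non-comparable between courses, and would usually make course 2 look worse. At 0.5 events per person-year with no true difference, the gap is at most 9.1% against 38.9%. It shrinks as single-course women fill course 1, nearly vanishes under the 30-day limit, and can turn if course 2 is cut short. These figures assume constant rates that the documents do not supply.

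A reader might infer that the table is bound to hide greater harm on re-exposure. The documents do not support that. Masking needs the literal reading, a cut-off course 2 set against long single-course follow-up, or a sizeable share of undated events. The undated rule can only lower the course-2 count, but by an unknown amount. Nor is course 2 the whole re-exposure group, since former active women are re-exposed in course 1. This is a low-cost improvement that should be made.

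**What to change.** In SAP 7.4:

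- Assign each TEAE to one course: onset on or after the first injection of course k and before the first injection of course k+1, or the end of study if there is none.
- Base the by-course table on one window for every course, from first injection to that course's Day 71 visit. Report later events separately per person-time.
- Add a paired display for women with two EN3835-202 courses.
- Split course 1 by EN3835 exposure in EN3835-201.
- Add a sensitivity table that places undeterminable events in course 2.

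The AE collection period in protocol 14.5.1 and in the schedules must also be reconciled, because the person-time table depends on it.

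With equal 73-day windows, an assumed 10% risk and a true doubling of the rate, the table would show 10.0% against 19.0%, the right direction and nearly the right size.

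The cost is SAP wording and a few extra tables from data already collected. The one drawback is that late events move out of the by-course table into a separate one.
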